16.4 Dual Energy X-ray Absorptiometry

A dual energy x-ray absorptiometry (DXA) scan is performed at Screening, Week 26 and Week 52, in order to collect relevant BMC/BMD data (including Z-scores) for whole body less head, and the lumbar spine. The scans of the distal forearm were removed from the original protocol at a later date, and hence data is limited.

All DXA data will be summarized separately for each scanner manufacturer (GE - Lunar Prodigy or Hologic – Discovery Horizon). Subjects who have results from more than one scanner type will be excluded from summaries, and their data will be listed only.

16.4.1 Whole Body Less Head and Lumbar Spine

The absolute values at Baseline, Week 26 and Week 52, and change from baseline at Week 26 and Week 52 will be summarized (n, mean, SD, median, 25th and 75th percentile, minimum, maximum) and presented by treatment group for the following measures of bone mineral content (BMC) and bone mineral density (BMD):

- Whole Body Less Head BMC (g)
- Whole Body Less Head BMD (g/cm^2)
- Whole Body BMC (g)
- Whole Body BMD (g/cm^2)
- Lumbar Spine BMC (g)
- Lumbar Spine BMD (g/cm^2)

BMD Z-scores will be provided in the DXA reports, and the absolute values at Baseline, Week 26 and Week 52, and change from baseline at Week 26 and Week 52 will be summarized (n, mean, SD, median, 25th and 75th percentile, minimum, maximum) and presented by treatment group and scanner for each of the following:

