2 SYNOPSIS

NAME OF COMPANY BioMarin Pharmaceutical Inc. [name]
 
NAME OF FINISHED PRODUCT: BMN 111
 
NAME OF ACTIVE INGREDIENT: Modified rhCNP
	
SUMMARY TABLE Referring to Part of the Dossier:
 
Volume:
 
Page:
 
Reference:
	
FOR NATIONAL AUTHORITY USE ONLY:

TITLE OF STUDY: A Phase 3 Randomized, Double-Blind, Placebo-Controlled, Multicenter Study to Evaluate the Efficacy and Safety of BMN 111 in Children with Achondroplasia
		

PROTOCOL NUMBER: 111-301
		

STUDY SITES: Approximately 33 clinical centers worldwide
		

PHASE OF DEVELOPMENT: Phase 3
		

STUDY RATIONALE:
 
Achondroplasia (ACH), the most common form of disproportionate short stature or dwarfism, is an autosomal dominant genetic skeletal disorder caused by a gain-of-function mutation in the fibroblast growth factor receptor-3 gene (FGFR3), a negative regulator of endochondral bone formation. Due to this FGFR3 mutation, there is exaggerated negative regulation on endochondral ossification, which results in ACH (Laederich, 2010).
 
The use of modified recombinant C-type natriuretic peptide (rhCNP) as a potential therapy for the treatment of ACH is based on the mechanism of action of C-type natriuretic peptide (CNP). CNP and its receptor, NPR-B, are key regulators of skeletal growth. CNP binding to its receptor, natriuretic peptide receptor-B (NPR-B), acts as a key regulator of longitudinal bone growth by down-regulating the mitogen-activated protein kinase (MAPK) pathway. CNP-mediated activation of NPR-B results in the rescue of the dwarfism phenotype of mice with a FGFR3 gain-of-function mutation (Yasoda, 2004; Yasoda 2009). The pharmacological activity of BMN 111 was explored in two mouse models of ACH, a severe, Fgfr3^{Y367C/+} model (Lorget, 2012), and a mild [Ach] ^{+/+} model. Partial or complete reversion of the ACH phenotype was observed in these mouse models after BMN 111 administration. Additionally, in wild-type mice, and normal rats and monkeys, BMN 111 administration resulted in growth plate expansion and dose-dependent skeletal growth at hemodynamically-tolerated dose levels (Wendt, 2015). Therefore, administration of CNP has been proposed as a therapeutic approach for ACH.
		

B:OMARIN[®]	Study 111-301 Amendment 4	Page 5
-----------------------------	---------------------------	--------

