8 STUDY OBJECTIVES

The primary objective of the study is to:

- Evaluate change from baseline in annualized growth velocity at 52 weeks in subjects treated with BMN 111 compared with control subjects in the placebo group.

The secondary objectives of the study are to:

- Evaluate change from baseline in height Z-score in subjects treated with BMN 111 compared with control subjects in the placebo group at 52 weeks.
- Evaluate change from baseline in upper:lower segment body ratio in subjects treated with BMN 111 compared with control subjects in the placebo group at 52 weeks.
- Evaluate change from baseline in body proportion ratios of the extremities.
- Evaluate effect of BMN 111 on bone morphology/quality by X-ray and DXA.
- Evaluate potential changes in HRQoL as measured by the QoLISSY and PedsQL questionnaires.
- Evaluate potential changes in functional independence as measured by the WeeFIM clinician-reported outcome.
- Evaluate safety and tolerability of BMN 111 in children with ACH.
- Evaluate the pharmacokinetics of BMN 111.
- Evaluate immunogenicity of BMN 111 and assess impact on safety, PK, and efficacy measures.
- Evaluate change from baseline in bone metabolism biomarkers.

The exploratory objectives of the study are to:

- Evaluate sleep study scores by polysomnography in a subset of subjects.
- Evaluate biomarkers of BMN 111 activity.
- Evaluate genomic biomarkers.

B:OMARIN[®]	Study 111-301 Amendment 4	Page 43
-----------------------------	---------------------------	---------

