14.4 Safety Analysis

All randomized subjects who receive at least one dose of double-blinded BMN 111 or placebo in this study will be included in the safety analysis. The safety analysis will be performed on safety population as defined in Section 14.7.2 and will be considered descriptive.

All AEs will be coded using the most current version of MedDRA will be used by the Sponsor to assign system organ class and preferred term classification to events and diseases, based on the original terms entered on the CRF.

All AEs will be coded using MedDRA. The incidence of AEs will be summarized by system organ class, preferred term, relationship to study treatment (as assessed by investigator), and severity. All AEs, including SAEs and AEs that lead to permanent discontinuation from the study and from the study treatment, will be listed. Hypersensitivity reactions and symptomatic hypotension are of interest, and the percentage of subjects who report these AEs will be presented. Hypersensitivity reactions will be defined in the SAP.

Clinical laboratory data will be summarized by the type of laboratory test. For each clinical laboratory test, descriptive statistics will be provided on baseline as well as all subsequent visits.

Descriptive statistics for other safety endpoints such as vital signs, ECG results, X-ray and DXA assessments of bone morphology and quality, clinical hip assessment, CBCL, anti-BMN 111 immunogenicity assessments, and bone metabolism biomarkers, will also be provided. Detailed statistical methods will be provided in the SAP. All other safety measures including laboratory tests, vital signs, ECG, X-ray and DXA assessments, clinical hip assessment, and anti-BMN 111 immunogenicity (discussed in the next section) will be summarized descriptively by group, listings will be provided for these safety endpoints.

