14.6 Determination of Sample Size

With 55 subjects planned in each of the two randomized groups (one BMN 111 dose group and one placebo group), the power to detect a difference of 1.75 cm/year between the BMN 111 group and the placebo group in change from baseline in AGV at 12 months is approximately 90%, assuming that the pooled standard deviation of the change from baseline in AGV is 2.80, using a two-sided two-sample t-test at a 0.05 significance level. The power calculation is based on data from Study 111-202 (a phase 2, open-label, sequential cohort dose-escalation study) and Study 111-901 (a natural history study for pediatric subjects with achondroplasia).

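### DXA results are compared between arms with no adjustment for bone size, so extra growth on BMN 111 will inflate BMC, may inflate areal BMD, and may mask a small density loss

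*SAP*

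**What the plan says.** SAP 16.4.1 summarises DXA at Baseline, Week 26 and Week 52, with change from baseline, "presented by treatment group for the following measures of bone mineral content (BMC) and bone mineral density (BMD"). The sites are whole body less head, whole body and lumbar spine. BMC is in grams and BMD is per unit of projected area, as in "Lumbar Spine BMD (g/cm^2"). For Z-scores the SAP says only that "BMD Z-scores will be provided in the DXA reports"; it names no reference and does not say whether they allow for height.

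The one refinement is in SAP 16.4: "All DXA data will be summarized separately for each scanner manufacturer". Neither document plans a height-adjusted Z-score, a volumetric estimate, or BMC adjusted for bone area or height.

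DXA has two roles. Protocol 8 makes it part of a secondary objective: "Evaluate effect of BMN 111 on bone morphology/quality by X-ray and DXA". Protocol 14.4 lists it among the descriptive safety endpoints: "X-ray and DXA assessments of bone morphology and quality, clinical hip assessment, CBCL".

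**The concern.** A longer bone of unchanged mineral density contains more mineral, so BMC rises with growth. A bone that is also deeper in the direction of the beam has more mineral behind each square centimetre, so areal BMD rises too. The Protocol Synopsis says that CNP, through its receptor, "acts as a key regulator of longitudinal bone growth", and the primary hypothesis is that BMN 111 children will outgrow placebo children. The placebo arm removes normal growth from the comparison but leaves the drug-induced part in.

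The arm difference in BMC, and possibly in areal BMD, therefore mixes growth with mineralisation, and the bias runs towards apparent benefit. DXA is the only planned assessment of bone density, and Protocol 7.1 reports adverse skeletal changes associated with exaggerated growth in animals with open growth plates. A small true loss of density is thus something that these tables should be able to show.

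**Working it through.** **The plan's own figure.** Protocol 14.6 gives "the power to detect a difference of 1.75 cm/year between the BMN 111 group and the placebo group" as about 90%, with 55 per arm, SD 2.80 and two-sided 0.05. The standardised difference is 1.75 / (2.80 × √(2/55)) = 3.28. Power is 90.6% by the normal approximation and 90.1% by the noncentral t with 108 df. The figure reproduces, so 1.75 cm/year is used as the design effect. No figure is stated for any DXA endpoint.

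**Inputs**
- Extra height at Week 52: 1.75 cm. Over exactly 364 days it is 1.75 × 364/365.25 = 1.74 cm, which makes no difference at the precision used here.
- Baseline height H: not given in the documents; assumed 90 to 120 cm. Protocol 7 gives average adult heights of 131 cm (men) and 124 cm (women).
- Placebo growth over the year: assumed 4 cm, the centre of the middle baseline-AGV band in SAP 14.7.
- Bone size is assumed to scale with standing height at every site.

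**Formulae, at constant true density.** The extra linear size is g = 1.75/(H + 4).
- Proportional growth: BMC scales as (1+g)³, projected area as (1+g)², areal BMD as (1+g).
- Length-only growth in the scan plane: BMC and area both scale as (1+g), so areal BMD is unchanged.
- Apparent density, BMC/area^1.5: unchanged under proportional growth; scales as (1+g)^−0.5 under length-only growth.

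| H (cm) | g | BMC, length-only | BMC, proportional | Areal BMD, length-only | Areal BMD, proportional | Apparent density, length-only |
|---|---|---|---|---|---|---|
| 90 | 1.75/94 = 1.86% | +1.9% | +5.7% | 0% | +1.9% | −0.9% |
| 105 | 1.75/109 = 1.61% | +1.6% | +4.9% | 0% | +1.6% | −0.8% |
| 120 | 1.75/124 = 1.41% | +1.4% | +4.3% | 0% | +1.4% | −0.7% |

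**Loss that could be hidden.** Under proportional growth, a true loss of 1 − 1/(1+g) leaves areal BMD unchanged: 1.4% at 120 cm and 1.8% at 90 cm. Under length-only growth, areal BMD hides nothing.

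**Z-scores.** If they are not height-adjusted, and the between-child SD of areal BMD is 10% to 15% of its mean (assumed), proportional growth shifts them by 1.41/15 = 0.09 to 1.86/10 = 0.19.

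**Precision.** With an assumed SD of 3% to 7% for percent change in areal BMD, the 95% half-width for the arm difference is 1.96 × SD × √(2/n). That is 1.1 to 2.6 percentage points with 55 per arm, and 1.6 to 3.7 with 27 per arm if the two scanner types split the trial evenly.

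**The case against.** A reader might infer that BMN 111 is bound to appear to raise BMD. The documents do not support that. They describe longitudinal growth and give no data on bone depth; if bones only lengthen, areal BMD does not move. A reader might also infer that the Z-scores rise with bone size. That may be so, but their reference is not stated and Protocol 9.12.6.4 leaves imaging detail to a central reader and vendor guidelines. What can be asked for is the reference.

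Standing height is also an uncertain proxy for the lumbar spine. The trial tests for a change in upper:lower segment ratio, so trunk and legs may not grow by the same percentage.

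Nor is bone quality judged by DXA alone. The plan includes limb lengths and tibial bowing (SAP 16.2), vertebral ratios and spine angles (SAP 16.3), bone biomarkers (SAP 17) and fractures (SAP 15.1.2; reportable within 24 hours under Protocol 10.1.3). These bear on bone health, but none of them measures density.

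Two further points stand. DXA carries no test or decision rule, and within a scanner subset a loss under 2% would be hard to resolve even with a perfect correction. And apparent density is not a neutral replacement for areal BMD: under length-only growth it shows a spurious fall of 0.7% to 0.9% in the active arm, a false safety signal.

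These points limit the size and certainty of the bias. They do not answer the BMC comparison, which is inflated under either geometry.

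**Conclusion.** The point holds as a moderate, inexpensive improvement. With no size adjustment, drug-induced growth will inflate the BMC comparison, by about 1.4% to 1.9% (length-only) up to 4.3% to 5.7% (proportional). It may inflate areal BMD, by 0% up to 1.4% to 1.9%, and at the upper end a true loss of about that size would be masked. The figures rest on the 1.75 cm design difference, assumed baseline heights of 90 to 120 cm, assumed placebo growth of 4 cm, and bone size scaling with standing height. Dividing by baseline height alone and widening it to 85 to 124 cm changes little: g becomes 1.4% to 2.1%.

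The primary and key secondary conclusions are unaffected, because DXA lies outside the confirmatory tests. A larger masked loss is not supported at 52 weeks under these assumptions, though the artefact would accumulate if the height difference between treated and untreated children kept widening.

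**What to change.** Keep the tables in SAP 16.4.1 and add one supplementary, descriptive, size-adjusted summary, run within scanner manufacturer as already planned.

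- **Lumbar spine:** derive bone area as BMC/BMD and apparent density as BMC/area^1.5, and show it beside areal BMD. State that apparent density is unbiased under proportional growth and areal BMD under length-only growth, so for growth between those two patterns they bracket the truth.
- **Whole body less head:** give the arm difference in Week 52 BMC adjusted for bone area or height at the same visit and for baseline BMC, for example on the log scale so that the size slope is estimated rather than fixed. Label it explanatory.
- **Z-scores:** state the reference used and whether it is height-adjusted. Do not footnote them as unadjusted unless that is confirmed.

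The cost is a few derived variables and one table; no new scans are needed. The downsides should be stated with it. The adjustment is approximate and its bias can run in either direction, the BMC model conditions on a post-baseline variable that treatment affects, and precision within scanner subsets will be limited.

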**Study 111-301 Statistical Analysis Plan**

- Whole Body Less Head BMD Z-Score
- Whole Body BMD Z-Score
- Lumbar Spine BMD Z-Score

The absolute values of total body percent fat, android percent fat, and gynoid percent fat at Baseline, Week 26 and Week 52 will be listed.

Box plots of whole body less head BMD Z-scores will be provided by treatment group, and scanner.

16.4.2 Regions of Interest in Distal Forearm

Due to sparsity of data, available data will be listed by treatment group, subject and visit. No summaries will be presented.

**Study 111-301 Statistical Analysis Plan****17 BONE METABOLISM BIOMARKERS**

Bone metabolism biomarkers will be collected to assess changes in bone metabolism. The safety population will be used for all summaries.

Samples for bone metabolism blood biomarkers (collagen X and bone-specific alkaline phosphatase [BSAP]) are collected pre-dose at Day 1, Week 13, Week 26, Week 39, Week 52 and at the Safety Follow-up visit.

For each biomarker, the absolute values, and change from baseline at Week 13, Week 26, Week 39, and Week 52 will be summarized (n, mean, SD, median, 25th and 75th percentile, minimum, maximum) and presented by treatment group.

For each biomarker, the change from baseline will also be summarized by visit in a box plot and presented by treatment group.

Bone metabolism biomarkers will be listed by treatment group and subject.

**Study 111-301 Statistical Analysis Plan****18 BMN 111 ACTIVITY URINE BIOMARKERS AND URINE CHEMISTRY**

Samples for BMN 111 activity urine biomarker, cyclic guanosine monophosphate [cGMP], and urine chemistry are collected pre-dose and 1, 2 and 4hr post-dose at Day 1, Day 2, Day 3, Week 6, Week 26, and Week 52. Each collection will be tested for biomarker concentration and urine creatinine concentration for normalization. The safety population will be used for all summaries.

The absolute values for pre-dose urine cGMP normalized by creatinine and urine chemistry (creatinine, potassium, sodium) results at each scheduled visit, and change from pre-dose to multiple post-dose time points at each scheduled visit will be summarized (n, mean, SD, median, 25th and 75th percentile, minimum, maximum) and presented by treatment group.

The absolute values for pre-dose urine cGMP normalized by creatinine and urine chemistry (creatinine, potassium, sodium) results at each scheduled visit, and the maximum change from pre-dose to post-dose will be summarized (n, mean, SD, median, 25th and 75th percentile, minimum, maximum) and presented by treatment group at each scheduled visit and overall.

The maximum change from pre-dose cGMP normalized by creatinine will also be summarized in a box plot by visit and presented by treatment group.

BMN 111 activity urine biomarkers will be listed by treatment group and subject.

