- m. A standard 12 lead ECG will include heart rate, rhythm, intervals, axis, conduction defects, and anatomic abnormalities. All ECGs will be performed in triplicate at the visits indicated in the Schedule of Events (Table 9.1.1). ECGs will be performed post-dose on study day visits at which a dose is given; in addition, on Day 1, ECGs will be performed pre-dose. On days when PK samples are being drawn, ECGs should be performed within a 5-minute window prior to 30-minute PK assessment
- n. Clinical labs (hematology, chemistry, and urinalysis) are all pre-dose collections.
- o. FSH/LH will be monitored for all subjects $>$ 8 years of age, and for subjects at Tanner stage 2 (whichever is earlier).

	Study 111-301 Amendment 4	Page 50
---	---------------------------	---------

- ^p Immunogenicity: Total and neutralizing anti-BMN 111 antibody samples (serum) will be drawn pre-dose on Day 1, Weeks 13, 26, 39, 52, and Safety Follow-Up or Early Termination visit as listed in the SOE. NAb testing and TAb testing for cross-reactivity with endogenous CNP, ANP or BNP will be performed only on Baseline and TAb positive samples. Blood (serum) samples for testing Total immunoglobulin E (IgE) and drug-specific IgE will be drawn on Day 1 and in the event of a Grade 3 or significant hypersensitivity adverse event, or at investigator or Sponsor discretion. The drug-specific IgE sample should be drawn at least 8 hr after the event start time or before the next dose. A sample for total IgE and serum tryptase should be drawn within 1 hour of the start of the event when possible or during the unscheduled safety visit.
- ^q Bone metabolism blood biomarker samples will be collected pre-dose on the indicated visits.
- ^r Bone metabolism urine biomarker samples will be collected as soon as possible upon arrival at the clinic. Each sample will be tested for biomarker concentration and creatinine concentration for normalization.
- ^s BMN 111 activity urine biomarker and urine chemistry samples will be collected pre-dose, and 1, 2, and 4 hr post-dose on the indicated visits (± 20 minutes for all urine sample time points). Each collection will be tested for biomarker concentration and urine creatinine concentration for normalization.

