9.4.4 Directions for Administration

Refer to the Study Drug Injection Guide for complete BMN 111 or placebo preparation instructions.

The injection will be administered as a daily dose of BMN 111 15 µg/kg or placebo given as a single subcutaneous injection. The dose should be given at approximately the same time every day whenever possible. Following administration of each dose, subjects will be observed for at least 2 hours after the injection for Days 1 to 3, and 30 minutes for all other dose administration days. Subjects should have adequate food intake prior to dosing. In the hour prior to injection, all subjects should have attempted to drink approximately 8-10 ounces or 240-300 mL of fluid (eg, water, milk, juice, etc).

Caregivers will administer BMN 111 or placebo at home once approved by the investigator and adequate training is demonstrated. Instructions on how to complete and document the training can be found in the Study Reference Manual. A caregiver will be eligible to administer BMN 111 or placebo if he or she meets all of the following criteria:

- The subject has been on a stable dosing regimen for a minimum of 3 days
- PI has approved administration of BMN 111 or placebo by the caregiver
- The caregiver has completed the Administration Training conducted by qualified study site personnel and has been observed by the study site personnel to be able to adequately prepare the proper dose and perform the injections safely

For dosing between planned clinic visits prior to caregiver approval, a home health nurse may administer BMN 111 or placebo, or subjects may be administered BMN 111 or placebo in the clinic by study staff or trained caregiver.

A subject's suitability for continued at-home drug administration will be evaluated by the investigator and the Sponsor's Medical Monitor if a subject experiences a Common Terminology Criteria for Adverse Events (CTCAE) Grade 3 or higher AE that is considered possibly or probably drug-related, and/or a hypersensitivity reaction during the study.

Contact by a study staff member to the caregiver will be required after the Week 6 visit every 4 weeks (± 10 days) when there are no study visits or contact in the preceding 4 weeks. During these contacts, study staff will ask the caregiver about dose administration and seek information on AEs and SAEs by specific questioning. Information on all AEs and SAEs should be recorded in the subject's medical record and on the AE eCRF.

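### SAP Section 18 summarises post-dose urine sodium and potassium without dilution correction, although creatinine is measured in every collection and already normalises cGMP

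*SAP*

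**What the plan says.** Protocol Table 9.1.1, footnote s, sets the sampling, with a window of 20 minutes either side of each time: "BMN 111 activity urine biomarker and urine chemistry samples will be collected pre-dose, and 1, 2, and 4 hr post-dose on the indicated visits". The same footnote adds: "Each collection will be tested for biomarker concentration and urine creatinine concentration for normalization". SAP Section 18 repeats both statements.

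SAP Section 18 then plans two summaries by treatment group. Both start from "The absolute values for pre-dose urine cGMP normalized by creatinine and urine chemistry (creatinine, potassium, sodium) results at each scheduled visit". The first continues with "change from pre-dose to multiple post-dose time points at each scheduled visit will be summarized". In the second, "the maximum change from pre-dose to post-dose will be summarized". The only figure concerns cGMP: "The maximum change from pre-dose cGMP normalized by creatinine will also be summarized in a box plot by visit".

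On fluids, Protocol 9.4.4 states: "In the hour prior to injection, all subjects should have attempted to drink approximately 8-10 ounces or 240-300 mL of fluid". Protocol 9.6 and 9.12.6.10 repeat this. It applies to both arms.

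Neither document plans a sodium/creatinine or potassium/creatinine ratio, a timed urine volume, osmolality or fractional excretion. Protocol Section 8 places the BMN 111 activity biomarkers among the exploratory objectives, and SAP Section 18 plans no hypothesis test.

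**The concern.** The concentration in a spot urine sample is the excretion rate divided by urine flow. A drink shortly before dosing can change flow over the hours in which the post-dose samples are taken, so a concentration can move while excretion stays the same. The plan accepts this for cGMP. It does so too for the bone metabolism urine markers, where footnote r of Table 9.1.1 says: "Each sample will be tested for biomarker concentration and creatinine concentration for normalization". Sodium and potassium come from the same collections as cGMP but receive no such correction.

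BMN 111 is an analogue of a natriuretic-family peptide (Protocol Section 7), so a reader of the table may well look to the sodium row for a renal effect. Scheduled clinical laboratory tests are pre-dose (Table 9.1.1, footnote n; SAP 15.2). These urine results are therefore the only scheduled post-dose electrolyte measurements in the two documents. What is at stake is what a row showing no difference, or a fall, can be taken to mean.

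**Working it through.** The plan gives no urine figures, so there is no stated number to reproduce. Step 1 is a reading of the text. Steps 2 to 4 are illustrations, and every physiological input in them is assumed.

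**1. Are sodium and potassium unnormalised?** In the SAP sentence the normalisation is attached to cGMP. Creatinine, potassium and sodium follow together in one bracket as urine chemistry. Creatinine cannot be normalised by itself, so the bracket cannot mean creatinine-normalised values. The SAP states no units, so this is an inference from the sentence, but a firm one.

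**2. Size of dilution within an arm.** With unchanged sodium excretion over 2 hours:

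post/pre concentration = basal volume / (basal volume + excreted part of the drink)

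Assume weight 15-40 kg, basal flow 0.5-1.5 mL/kg/h, and 25-75% of a 240-300 mL drink excreted in 2 hours.

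- Least dilution: basal 40 × 1.5 × 2 = 120 mL; drink 0.25 × 240 = 60 mL; 120/180 = 0.67.
- Most dilution: basal 15 × 0.5 × 2 = 15 mL; drink 0.75 × 300 = 225 mL; 15/240 = 0.06.

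Under these inputs, concentration falls to between 0.06 and 0.67 of its pre-dose value with no change in excretion. The documents do not say whether the pre-dose urine is passed before or after the drink. If after, the baseline may be diluted too and the fall is smaller.

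**3. Between arms, drug has no effect on urine volume.** Dilution is the same on average in both arms and cancels, so a true rise of 30% in sodium excretion reads as a ratio of 1.30 either way. What changes is precision. Assume 55 per arm, a log-SD of 0.4 for the change in sodium excretion, 0.15 for creatinine excretion, and s for dilution.

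- SD of raw log change = √(0.4² + s²): 0.50, 0.72 and 0.98 for s = 0.3, 0.6 and 0.9.
- SD of the log sodium/creatinine change = √(0.4² + 0.15²) = 0.43, whatever s is.
- Ratio of SDs, and so of confidence interval widths: 1.17, 1.69 and 2.31.

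In a simulation with the same inputs (1,500 replicates), a two-sample t-test gave p < 0.05 in 0.78, 0.46 and 0.29 of trials on raw values, against 0.88 to 0.89 on the ratio. The SAP plans no such test; these figures only express how much clarity is lost.

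**4. Between arms, drug changes urine volume.** If the drug multiplies sodium excretion by E and volume by V, and leaves creatinine excretion alone, the raw between-arm ratio is E/V and the normalised ratio is E.

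| E | V | Raw | Normalised |
|---|---|---|---|
| 1.30 | 1.00 | 1.30 | 1.30 |
| 1.30 | 1.15 | 1.13 | 1.30 |
| 1.30 | 1.30 | 1.00 | 1.30 |
| 1.00 | 1.30 | 0.77 | 1.00 |

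The third row is a masked effect and the fourth a false fall. The simulated ratios agree. All of this is on the ratio scale, whereas the SAP summarises arithmetic changes; the direction of the problem is the same.

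**The case against.** The strongest reply is that this is a randomised, double-blind comparison with every summary shown by arm. The fluid request reaches both arms alike, so it cannot confound BMN 111 against placebo. That stands. A reader might infer from the drink alone that the comparison is biased, or that the table will hide a natriuresis. The documents support neither: bias requires the drug to change urine volume, and neither document reports or predicts that it does. The request is also only that subjects should have attempted to drink, and sampling runs from roughly 1 to 5 hours after drinking.

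Purpose is a second reply. Neither document says that urine sodium or potassium is there to detect natriuresis, and the named activity marker, cGMP, is normalised. This stands, and it limits the importance of the point. A reader might cite the SAP Section 19 listing that mentions fluid and electrolyte imbalance as evidence of a renal sodium concern. That listing is about cross-reactive antibodies and adverse events, and does not show this.

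A third reply is that raw urine creatinine is summarised beside sodium and potassium, so dilution is visible at group level. This stands in part. Separate group summaries do not give the within-subject ratio, and the maximum change for sodium and for creatinine may come from different time points. It is, however, a good reason to keep the raw creatinine summary.

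Finally, SAP Section 20 refers exposure-response work to a separate Clinical Pharmacology Analysis Plan, which is not among these documents and may treat the electrolytes differently.

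**Conclusion.** The point holds as an improvement to a descriptive, exploratory table. Urine sodium and potassium have no planned dilution correction, while the means to correct them is measured in the same collections and applied to cGMP in the same sentence. Within-arm changes from pre-dose cannot be read as changes in excretion. The between-arm comparison is not biased by the drink but is less precise, with intervals 1.17 to 2.31 times as wide under the assumed variances. Masking or a false fall would arise only with a drug effect on urine volume, and its size depends wholly on the assumed E and V. The ratio itself assumes that the drug leaves creatinine excretion unchanged. No primary, key secondary or confirmatory result is touched.

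**What to change.** In SAP Section 18, add sodium/creatinine and potassium/creatinine ratios, computed within each collection. Summarise them by arm in the same way as normalised cGMP: pre-dose value, change to 1, 2 and 4 hours, and maximum change. Keep the raw sodium, potassium and creatinine summaries beside them, since raw creatinine shows group-level dilution. State whether the pre-dose urine is collected before or after the drink, so that the baseline can be interpreted.

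The cost is a few lines of SAP text, written before unblinding, and two derived variables from results already collected. No new samples, visits or assays are needed.
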